Various studies have evaluated the outcomes of different closure devices, however, there are no reports assessing the length of closure times using DERMABOND PRINEO (Ethicon, Johnson and Johnson, Somerville, New Jersey) Knotless Tissue Control Devices during superficial closure in orthopaedic surgery. Huemer et al.(1) performed an observational study of 180 patients who had 224 excisional body-contouring surgeries utilizing Dermabond Prineo for superficial closure. Authors concluded that this closure type enables the surgeon to perform a quick and smooth skin closure. However, 4 patients (1.8%) developed local allergic reactions, which necessitated early removal and topical corticosteroid treatment. Parvizi et al.(2) performed an open, prospective, randomized clinical study of superficial wound closure on 60 patients undergoing abdominoplasty with either Dermabond Prineo or conventional superficial closure. They found significantly lower price (\$134.79 cheaper) and significantly better Hollander Cosmesis Scale scores in Dermabond Prineo cohort. In addition, there was a significantly better cosmetic outcome at 6 and 12 months after surgery. The use of Dermabond Prineo may be able to decrease operative time and costs in other surgical fields, such as orthopedics. Careful patient allergy history is necessary to avoid adhesive allergic reactions.

Regulatory Sponsor:

This study is an Investigator Initiated research trial. Each study site will be considered its own regulatory sponsor and is responsible for internal data monitoring and any study reporting required by ClinicalTrials.gov.

Study Design:

In this prospective pilot study examining the superficial closure during total knee arthroplasty, active subjects will receive the STRATAFIX Spiral Knotless Tissue Control Device for subcuticular closure in addition to DERMABOND PRINEO (Ethicon, Johnson and Johnson, Somerville, New Jersey) system for dermal closure. The control subjects will receive staples (standard-of-care).

The purpose of this study is to compare end points (see below):

- **The primary endpoint of the study** will be cosmesis observation using the modified Hollander scale (Table1).
- **Secondary endpoints** will examine: wound closure time, patient satisfaction with wound appearance, wound related complications, cost comparison including time and materials

As a pilot study, hypothesis testing will not be performed.

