Post-operatively, patients will be assessed at clinic visits at 6 weeks and 3 months. At these time points, we will assess (**Table 2**):

- Incidence of any wound complications
- Wound appearance using the Hollander cosmesis questionnaire (**Table 1**)
- Patient satisfaction with wound appearance using visual analogue scale (VAS)

Table 1. Hollander cosmesis questionnaire	
Stepoff borders	0 for yes, 1 for no
Contour irregularity – puckering	0 for yes, 1 for no
Scar width – greater than 2mm	0 for yes, 1 for no
Edge inversion – sinking, curling	0 for yes, 1 for no
Inflammation – redness, discharge	0 for yes, 1 for no
Overall cosmesis	0 = poor, 1 = acceptable

Table 2: Research Procedures				
REQUIRED STUDIES	Pre-Op	Intra-operative	6 weeks post-op	3 months post-op
Informed Consent	x			
Length of surgery		x		
Length of closure time		x		
Amount of suture material used		x		
Surgeon experience level		x		
Incidence of wound complications			x	x
Hollander cosmesis questionnaire			x	x
Patient satisfaction with wound appearance (VAS)			x	x

Methods

- A prospective randomized pilot study

Sample

- 60 subjects for a pilot study

Inclusion Criteria:

1. Males and females, between the ages of 18 to 80 years at the time of signing the informed consent document.
2. Understand and voluntarily sign an informed consent document prior to any study-related assessments/procedures are conducted.
3. Able to adhere to the study visit schedule and other protocol requirements.
4. Able to fluently speak and understand the local language
5. If female, is nonpregnant (negative pregnancy test results at the baseline/randomization visit) and nonlactating.
6. End-stage osteoarthritis patients planning to undergo primary total knee arthroplasty
7. BMI less than 40 kg/m²

Exclusion Criteria:

1. BMI greater than or equal to 40 kg/m²
2. History of known bleeding disorder

3. History of medical co-morbidity that may result in poor wound healing (ie. diabetes mellitus, peripheral vascular disease)
4. Patients <18 or >80 years of age
5. Patients who are prisoners
6. Mentally unable to sign informed consent
7. Has an uncontrolled illness that, in the opinion of the investigator, is likely to cause the patient to be withdrawn from the trial or would otherwise interfere with interpreting the results of the study.

Screening and Recruitment: Informed Consent

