Patients will be randomized to either arm of the study as follows: sealed envelopes in a random order will be used to place study participants in either the active arm or in the control arm of the study. Patients will be randomized in a one to one ratio. At the commencement of each arthroplasty, a random envelope will be drawn which dictated the type of suture to be used, thus blinding the patients to the type of suture they received.

Research Procedure:

A medial parapatellar approach will be performed. All closures will be performed in 3 layers, with the knee in approximately 90° of flexion to minimize potential imbrication of the capsule. For the traditional closure (control group), the arthrotomy (deep layer) is repaired using number 1 Vicryl followed by closure of the intermediate layer with a 2-0 Vicryl and the skin will be closed with staples (Standard of care).

For the active arm of the study, the arthrotomy (deep layer) is repaired using number 1 Vicryl, the subcutaneous layer will be then closed with simple interrupted knots using number 2-0 braided absorbable sutures (Vicryl), followed by closure of the subcutaneous layer using a STRATAFIX Spiral Knotless Tissue Control Device in addition to DERMABOND PRINEO (Ethicon, Johnson and Johnson, Somerville, New Jersey) system for dermal closure. (See table 3).

Closure with the bidirectional barbed suture involves starting at the midpoint of the wound and proceeded simultaneously both proximally and distally to the ends. At the ends of the wounds, the suture is backstitched at this subcuticular level (2-3 throws) toward the midpoint for further reinforcement before bringing the needle out through the skin; the suture is then cut flush with the skin tissue at its free end. With each throw, the leading end of the suture is pulled with only enough tension to engage the barbs with the surrounding tissue, thereby locking the wound edges into approximation. As with the traditional closure and in concordance with our routine protocol, skin will be closed with staples.

Table 2: Suture Type for Closure Following Total Knee Arthroplasty.		
Layer	Control Group	Active Group
Capsule	Vicryl #1 (J947H#1)	Vicryl #1 (J947H#1)
Subcutaneous	Vicryl 2.0 (J945H 2-0)	Vicryl 2.0 (J945H 2-0)
Subcuticular	Staples	STRATIFIX Spiral Knotless tissue control device (undyed)
Skin		DERMABOND PRINEO

Patient Protection:

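### Drawing the envelope at surgery does not blind patients afterwards, and neither the scorer of the primary Hollander endpoint nor that scorer's blinding status is specified

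*Combined protocol and SAP*

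**What the plan says.** **Allocation and blinding.** Under Randomization procedures, "sealed envelopes in a random order will be used" to assign patients 1:1. One is drawn as each operation begins, "which dictated the type of suture to be used, thus blinding the patients to the type of suture they received". This is the only mention of blinding in the available text.

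**What differs at the skin.** Study Design gives the active arm STRATAFIX plus DERMABOND PRINEO, and then: "The control subjects will receive staples (standard-of-care)". The active-arm paragraph and the suture-type table under Research Procedure say the same. The paragraph on barbed-suture technique, however, ends: "As with the traditional closure and in concordance with our routine protocol, skin will be closed with staples".

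**What is rated.** The primary endpoint "will be cosmesis observation using the modified Hollander scale (Table1)". For the visits at 6 weeks and 3 months the plan says "At these time points, we will assess" and lists wound complications, "Wound appearance using the Hollander cosmesis questionnaire" and "Patient satisfaction with wound appearance using visual analogue scale (VAS)". Neither that list nor the visit schedule says who fills in the Hollander form or whether that person knows the arm.

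**The concern.** Concealing an allocation and blinding a patient are different things. The first protects enrolment and ends when the envelope is opened. The second has to last until the patient rates the wound, up to 3 months later. The plan derives the second from the first.

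Two endpoints are exposed:

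- **Patient VAS (secondary).** Reported as patient-blinded, it would look less open to expectation than the design makes it.
- **Hollander form (primary).** An observer scores it. A scorer who knows the arm and expects one closure to look better can score the arms differently. Randomization gives no protection against that, because it happens after allocation.

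A descriptive pilot is exposed too, since a biased difference misleads with or without a p-value. Study Design rules out hypothesis testing while Data Analysis sets a 0.05 threshold; that conflict is a separate matter, and this point does not depend on it.

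**Working it through.** **1. Does the stated mechanism blind patients?** The plan gives no figure here, so the texts are set side by side.

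| Needed for patient blinding | In the plan |
|---|---|
| Arm unknown before surgery | Yes, if the sealed envelopes are used as described |
| Arm not disclosed after surgery | No instruction |
| Wound covered or made to look alike | No procedure |
| Same visible closure in both arms | Different in Study Design, the active-arm paragraph and the suture table; staples in the closing sentence of the technique paragraph |

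Only the first row is met. The last row is internally contradictory, so it cannot be used to show masking. Even if reconciliation made the skin look alike, the draw alone would not keep patients unaware, so the inference fails either way.

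**2. Is the Hollander scorer protected from knowing the arm?** The only subject given is a collective first person. De-identified sheets (Patient Protection) hide who the patient is, not which arm. The visit schedule has closure time and suture material recorded during surgery, so whoever records them knows the arm; that person is not named either. In Table 1, five of the six items ask whether a feature is present and one is a global opinion. The models in Data Analysis adjust for BMI, gender, age and ethnicity. None of these measures the scorer's knowledge, so adjustment cannot remove differential scoring.

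**3. How large could it be?** The documents give nothing to estimate this from. The following is an illustration only.

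From the plan: 60 subjects at 1:1, so 30 per arm; six 0/1 items; two-sided 0.05.

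Assumed: the items are summed to a 0–6 score (the plan defines no total); each item passes with probability p = 0.80 to 0.90; within-patient correlation is 0.3; there is no true effect; a fraction f of failing items is scored as passing in the active arm only; pooled t-test; beta-binomial scores, 100,000 simulated trials per case.

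- Shift in the mean difference = 6 × (1 − p) × f. For p = 0.80 and f = 0.25: 6 × 0.20 × 0.25 = 0.30.
- SD = √[6p(1 − p)(1 + 5 × 0.3)]. For p = 0.80: √(0.96 × 2.5) = 1.55. For p = 0.85 and 0.90: 1.38 and 1.16.
- 95% half-width with no differential scoring ≈ 2.00 × SD × √(2/30): about 0.80, 0.71 and 0.60.

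| Failing items changed | Shift (points) | Rate of p ≤ 0.05 | Coverage of 95% interval |
|---|---|---|---|
| None | 0 | about 5% | about 95% |
| 5–10% | 0.03–0.12 | 5–6% | 94–95% |
| 25% | 0.15–0.30 | 7–12% | 88–93% |
| 25–50%, set to give a 0.30 shift | 0.30 | 12–19% | 81–88% |
| Global item only, 25% | 0.025–0.05 | about 5% | about 95% |
| Global item only, all | 0.10–0.20 | 6–8% | 92–94% |

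With correlation from 0.1 to 0.5, the all-item rates become 5–7% (5–10% changed), 6–17% (25% changed) and 10–32% (0.30 shift).

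**The case against.** **The bias may be negligible for a pilot.** A shift of 0.03–0.12 points is small beside a half-width of 0.60–0.80. A visible effect needs a quarter or more of all failing items changed, always in one direction, including a scar-width item with a 2 mm threshold. No figure in the documents supports that. This stands, and it limits the weight of the point. It does not supply the missing safeguard.

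**Silence is not unblinded scoring.** A reader might infer that the operating surgeon will score the wounds, or that assessors are unblinded. The documents do not say so. The surgeon is not excluded, but only by omission. Nor do they say whether the arm can be recognised at 6 weeks or 3 months. The fair reading is that assessor blinding is not specified.

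**The staples sentence could mean the wounds look alike.** Read literally, it does. It conflicts with Study Design, the active-arm paragraph and the suture table, so it cannot be relied on. It makes the open-label reading of the VAS conditional on reconciliation, but it does not rescue the inference from the envelope.

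**Naming which staff must score may be impractical.** The documents do not establish staffing. The fix therefore needs a fallback.

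**Conclusion.** The point holds at moderate severity. Two findings rest on the text alone: the patient-blinding statement does not follow from the procedure described, and the role and blinding status of the primary-endpoint scorer are unspecified. On the closures given in Study Design, the active-arm paragraph and the suture table, the VAS should be treated as open-label unless a real masking procedure is added.

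Bias is possible, not demonstrated, and its size is unknown. A reader might take the 12–19% or 10–32% rates as a forecast for this trial. They are not: they require a summed score that the plan does not define and large one-directional scoring differences that no document figure supports. Under the same assumptions, small differences leave the error rate close to nominal.

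This covers the available text, from which one passage had been removed.

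**What to change.** 1. Reconcile the skin-closure statements in Study Design, the active-arm paragraph, the suture table and the end of the technique paragraph.
2. Whatever the result, delete the inference that the draw blinds patients. Say that the envelope conceals allocation until surgery. Then either describe a procedure that keeps patients unaware until the 3-month rating, or state that patients are not blinded and report the VAS as open-label.
3. State that at 6 weeks and 3 months the Hollander form, and the wound-complication assessment where feasible, is completed by an existing coordinator or co-investigator who was not in the operating room for that patient and did not record the closure data, and not by the operating surgeon. If no such person is available, report the assessment as unblinded.
4. Add one line to the form for the scorer's role and whether the scorer knew the arm.

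**Cost.** A few sentences and one form line, plus some scheduling effort. No new staff or visits are needed if, as assumed, a suitable person already exists; the Informed Consent section shows that coordinators and co-investigators are part of the study. Residual marks or a patient's remark may reveal the arm, so blinding may be only partial and must be reported as such.

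### The barbed-suture technique paragraph ends by stapling the skin, while three other statements give the active arm DERMABOND PRINEO there and name staples only for control

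*Combined protocol and SAP*

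**What the plan says.** Study Design states that "active subjects will receive the STRATAFIX Spiral Knotless Tissue Control Device for subcuticular closure in addition to DERMABOND PRINEO", the latter for the dermal closure. For the comparator it states: "The control subjects will receive staples (standard-of-care").

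Research Procedure then sets out the operation by arm. The control paragraph opens "For the traditional closure (control group") and describes Vicryl for the deep and intermediate layers and staples at the skin. The active-arm paragraph describes Vicryl for the deep and subcutaneous layers, "followed by closure of the subcutaneous layer using a STRATAFIX Spiral Knotless Tissue Control Device in addition to DERMABOND PRINEO", again for dermal closure. It does not mention staples.

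A technique paragraph for the bidirectional barbed suture follows. It explains how the suture runs from the midpoint to both ends of the wound and how, at the ends, "the suture is backstitched at this subcuticular level (2-3 throws) toward the midpoint". Its last sentence reads: "As with the traditional closure and in concordance with our routine protocol, skin will be closed with staples".

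The suture table comes directly after. Its Active Group column lists the STRATAFIX device at the subcuticular level and DERMABOND PRINEO at the skin. Staples appear only in the Control Group column.

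**The concern.** Skin closure is central to what is being randomized, so the protocol has to give one description of it for each arm. Here the closing sentence of the only step-by-step account of the technique tells the surgeon to staple, and it appeals to the routine protocol in doing so. The other three statements describe the same arm without staples.

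The sentence is also incomplete. It does not say whether staples take the place of PRINEO or go on as well. Under either reading, a trial designed to compare an alternative with staples would become a trial in which both arms are stapled.

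The primary endpoint is wound cosmesis on the modified Hollander scale. The secondary endpoints are closure time, patient satisfaction with wound appearance, wound complications and cost of time and materials. Each depends on how the skin was closed, so an active arm with an uncertain or mixed skin closure would make all of them hard to interpret.

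**Working it through.** No figure in the plan needs reproducing. The check sets every statement of skin closure side by side.

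| Place | Arm | Skin closure |
|---|---|---|
| Study Design | Active | STRATAFIX (subcuticular) plus PRINEO |
| Study Design | Control | Staples |
| Research Procedure, control paragraph | Control | Staples |
| Research Procedure, active-arm paragraph | Active | STRATAFIX plus PRINEO |
| Research Procedure, technique paragraph | Not labelled | Staples |
| Suture table | Active | STRATAFIX (subcuticular), PRINEO (skin) |
| Suture table | Control | Staples |

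**Step 1: which arm the technique paragraph concerns.** The paragraph does not name an arm, and the documents do not call STRATAFIX barbed, so this is an inference. Four features of the text support it.

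- Research Procedure uses the term traditional closure for the control group. A closure likened to the traditional one is being set against control.
- The paragraph describes a suture at the subcuticular level. Control receives only Vicryl and staples; the only suture the table lists at that level is STRATAFIX, in the active column.
- STRATAFIX is the only non-Vicryl suture in either arm.
- The paragraph comes immediately after the active-arm paragraph.

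Reading the sentence as applying to both arms does not remove the conflict, because active-arm skin would still be stapled.

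**Step 2: count.** Three statements give the active arm PRINEO without staples (Study Design, active-arm paragraph, suture table). One gives staples (end of the technique paragraph). No other text reconciles them or says which takes precedence.

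**Step 3: what would differ between the arms above the shared Vicryl layers.**

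- Three concordant statements: {STRATAFIX, PRINEO} versus {staples}. Three products differ.
- Staples in place of PRINEO: {STRATAFIX, staples} versus {staples}. One product differs, STRATAFIX.
- Staples added to PRINEO: {STRATAFIX, PRINEO, staples} versus {staples}. Two products differ, and staples are common to both arms.

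These counts show how the contrast changes. They do not measure bias.

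**Step 4: how many subjects are affected.** The Sample entry gives 60 subjects and Randomization procedures gives a one-to-one ratio: 60 × 1/2 = 30, approximately, in the active arm.

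**Step 5: whether the cross-reference settles it.** The active-arm paragraph points elsewhere: "system for dermal closure. (See table 3"). No table in the text provided has that number. The suture table is headed "Table 2: Suture Type for Closure Following Total Knee Arthroplasty", a number already given to the schedule of research procedures. A reader can guess which table is meant, but the pointer does not resolve as written.

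**The case against.** The strongest reply is that a careful reader can see which statement is the outlier. Three statements agree, and the suture table, which assigns products by arm, comes straight after the conflicting sentence. The documents give no sign of how often a surgeon would follow that sentence over the others, so the harm is conditional. Study Design also says that this is a pilot without hypothesis testing, which lowers the stakes of any bias.

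Part of this stands. The frequency is unknown, no bias can be calculated, and assigning the paragraph to the active arm is an inference.

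The rest does not remove the problem. A majority of statements is not a precedence rule, and the outlying sentence is an operative instruction that invokes routine practice. Descriptive pilot results are as hard to interpret as tested ones if the active treatment is not fixed, and Data Analysis in any case sets a two-sided significance threshold of 0.05. The randomization envelope is said to dictate the closure, but its contents are not shown, so it cannot be relied on to settle the matter.

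**Conclusion.** The concern holds. The protocol contradicts itself on the skin closure of the active arm, and nothing in it resolves the contradiction. It must be fixed, because it concerns the definition of the randomized intervention.

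Its effect on the results cannot be sized: neither the magnitude nor the direction of bias follows from the documents. What can be said is that the sentence governs about 30 of 60 subjects and that, if followed, it leaves both arms stapled. The conclusion rests on reading the technique paragraph as including the active arm, which the text strongly supports and which a both-arms reading also satisfies. The harm depends on the sentence being followed in practice.

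**What to change.** Reconcile the last sentence of the technique paragraph with Study Design, the active-arm paragraph and the suture table, so that a single description of the active-arm skin closure appears in all four places. Which closure is intended is for the investigators to state; this review does not choose. Label the technique paragraph with the arm it describes.

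Three editorial points can be settled in the same edit: the table number cited by the active-arm paragraph; the statement that all closures have three layers, given four levels in the active column (the count depends on whether PRINEO is a layer); and the name of the STRATAFIX layer, which the active-arm paragraph gives as subcutaneous and the other places as subcuticular.

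Record the skin closure actually used for each operation, so that departures can be counted and reported. The schedule of research procedures lists the amount of suture material among the intra-operative data but not the type of skin closure. The data form is not in the documents and may already capture this.

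The cost is a wording amendment and at most one form field, with no additional patients or procedures.

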- Cancer: Not related and unexpected within 10 working days from discovery/awareness

b) External Death:

Related/possibly related and unexpected – within 5 working days from discovery/awareness not related whether expected or unexpected – at time of continuing review related/possibly related and expected – at time of continuing review

c) ALL Deaths are also reported at time of continuing review using the AE summary log.

4. Non-serious Adverse events (Internal and External) that are both Related/Possibly related and unexpected are reported on the AE Summary Log at time of continuing review to assess trends.

5. An IRB staff (a qualified, licensed practitioner assigned to this function by the IRB chair and IRB Executive Director) reviews Adverse Event Reports to determine whether they represent Unanticipated Problem Involving Risks to Participants or Others. Events that are assessed, by either the IRB Staff or Investigator, to place subjects or others at a greater risk of harm than was previously known or recognized, or changes the risk/benefit ratio of the study, or requires a change in the protocol and/or consent document are referred to Full Board for review under Policy #70. Events that do not involve risk to Participants or Others or changes to the

informed consent or protocol do not require further review. Investigators are informed of the determination and the IRB file is updated.

6. The AE Summary Log is reviewed by the IRB at the time of continuing review to identify trends in frequency and severity which may impact subject safety.

This study is an Investigator Initiated research trial. Each study site will be considered its own regulatory sponsor and is responsible for internal data monitoring and any study reporting required by ClinicalTrials.gov.

Data Analysis:

Unless otherwise indicated, all testing of statistical significance will be two-sided, and a difference resulting in a p-value of less than or equal to 0.05 will be considered statistically significant. Also, after each analysis, General Linear Models (GLM) will be used to control for possible confounders, including BMI, gender, age and ethnicity.

References

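### Study Design rules out hypothesis testing while Data Analysis sets a two-sided p≤0.05 rule, and neither a primary Hollander visit nor a primary estimate is named

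*Combined protocol and SAP*

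**What the plan says.** Four parts of the combined protocol and SAP bear on this point.

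- **Study Design, after the endpoints:** "As a pilot study, hypothesis testing will not be performed". The sentence covers the whole study and makes no exception.
- **Data Analysis:** the section opens with sidedness: "Unless otherwise indicated, all testing of statistical significance will be two-sided". For the threshold, its rule is that "a difference resulting in a p-value of less than or equal to 0.05 will be considered statistically significant". It then adds a second layer of analysis: "Also, after each analysis, General Linear Models (GLM) will be used". The covariates it names are BMI, gender, age and ethnicity. These two sentences are the whole analysis plan.
- **Primary endpoint (Study Design):** it "will be cosmesis observation using the modified Hollander scale". No visit and no summary measure is given. On follow-up, the plan says "Post-operatively, patients will be assessed at clinic visits at 6 weeks and 3 months", and lists "Wound appearance using the Hollander cosmesis questionnaire" among the assessments at those time points. Table 2 (Research Procedures) marks the questionnaire at both visits equally. Table 1 lists six items, each scored 0 or 1, without saying how they combine.
- **Sample and Randomization procedures:** "60 subjects for a pilot study", allocated one to one, which implies 30 per arm.

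**The concern.** An analyst cannot follow both statements. Under Study Design no test is run. Under Data Analysis tests are run and a p-value of 0.05 or less is declared significant. No text calls the p-values descriptive, limits them to secondary endpoints, or says which statement governs.

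The undefined primary result makes this worse. Two visits, each with an unadjusted and a model-adjusted comparison, give at least four candidate results for the primary endpoint. The word that introduces the covariates (*including*) can also be read as leaving the list open. A reader of the final report could not tell whether a reported p≤0.05 was a planned test or one of several possible results in a pilot. The gap matters even if no test is run, because a pilot that reports only estimates still has to say which one is primary.

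**Working it through.** **1. Can the statements be read together?** The only candidate link is the qualifier that opens the Data Analysis sentence. That sentence sets sidedness and a threshold, so its natural scope is exceptions to those, and it presupposes that tests take place. The Study Design statement has no exceptions. If it overrode the rule entirely, the rule would govern nothing. The two remain in conflict.

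**2. The plan's own figure.** The total of 60 is given without power, effect size, standard deviation or dropout, so it cannot be reproduced. This point does not dispute it.

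**3. Inputs.** From the documents: threshold 0.05, two-sided; two visits; two results per visit; 60 subjects at 1:1, so 30 per arm; covariates BMI, gender, age and ethnicity. Assumed, because the documents give neither: the between-visit correlation ρ (0.5, 0.8, 0.9) and the share R² of outcome variance that the covariates explain (0 to 0.3).

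**4. Reference values if results were independent.** Two visits: 1 − 0.95² = 9.75%. Four results: 1 − 0.95⁴ = 18.5%. The second overstates the risk because the four results are correlated.

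**5. Two visits, unadjusted.** With bivariate normal test statistics, the false-positive rate is 1 − P(|Z₁| < 1.96, |Z₂| < 1.96):

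| ρ | Rate |
|---|---|
| 0.5 | 9.07% |
| 0.8 | 7.81% |
| 0.9 | 7.04% |

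**6. Two visits, unadjusted or adjusted.** Simulation with no true difference: 30 per arm, a t-test and a linear model with four covariates (BMI, gender, age, one ethnicity indicator), 100,000 trials per cell, Monte Carlo standard error about 0.1 percentage point. Chance that any of the four results reaches p≤0.05:

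| ρ | R² = 0 | 0.1 | 0.2 | 0.3 |
|---|---|---|---|---|
| 0.5 | 11.0% | 12.2% | 13.4% | 13.9% |
| 0.8 | 9.6% | 10.8% | 11.6% | 12.1% |
| 0.9 | 8.5% | 9.6% | 10.3% | 11.1% |

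Repeat simulations under the same kind of assumptions gave 8.5% to 14.4% overall. With an assumed 25 per arm the range is 8.8% to 14.1%.

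**7. What each choice removes.** Naming the visit but leaving the estimate open gives 6.0% to 7.8%. Naming both gives 4.8% to 5.1%, which is the nominal level within simulation error.

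**8. Check on a bounded score.** Taking the endpoint as a sum of six 0/1 items (assumed; favourable probability 0.70 to 0.95 per item, latent ρ 0.5 or 0.9, latent R² 0.2, 20,000 trials) gives 8.0% to 9.3% for two visits unadjusted and 11.3% to 13.1% for any of four. The normal approximation does not drive the result.

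**9. Precision if no test is run.** With 30 per arm and no dropout, the 95% interval for a mean difference has half-width 1.96 × √(2/30) = 0.51 standard deviations.

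**The case against.** The strongest defence is that the Data Analysis wording is generic text that yields to the specific design statement: it allows for exceptions, and Study Design states one with a reason. This may well explain how the wording arose. It does not settle the matter, because the reader must infer it and the rule is then left with nothing to apply to.

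The percentages are also conditional. They assume that the no-testing statement is set aside and that any one significant result counts as success, and the plan sets no such success rule. If all four results were reported side by side, a reader could see the selection. That is fair: the figures illustrate the room for choice, and the contradiction stands without them.

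The adjusted model can be read as a follow-up to a main unadjusted analysis, and the covariate list as complete. Both readings are possible, but the plan states neither.

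Finally, a 95% interval that excludes zero carries nearly the same information as p≤0.05, so deleting the rule alone changes little in practice. This also stands. Naming the visit, the score and the estimate is what restricts choice, and the named estimate cannot be computed until the six items are combined in a stated way.

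**Conclusion.** The plan is wrong as written and should be fixed. The contradiction rests on the text alone and needs no assumption. On the primary score, acting on the Data Analysis rule would permit significance claims that the design disclaims, with a false-positive rate of 7.0% to 9.1% over two unadjusted visits and 8.5% to 13.9% over all four results (11.6% at ρ = 0.8 and R² = 0.2). Those figures depend on the assumed correlations and covariate strength and on counting any success. The inflation is moderate and this is a 60-subject pilot, so the defect lies in how results can be interpreted; it does not invalidate the trial. Pilot status may explain why there is no power calculation, but it does not explain two incompatible statements about testing.

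**What to change.** To match the Study Design statement, delete the p≤0.05 rule and replace it with wording such as:

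> Each endpoint will be reported as a between-arm estimate with a 95% confidence interval; no significance claim will be made. The primary estimate is the between-arm difference in Hollander score at [6 weeks or 3 months], [unadjusted, or GLM-adjusted for BMI, gender, age and ethnicity only]. The other visit, the other estimate and the secondary endpoints are supportive.

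The sponsor fills both brackets; the documents favour neither visit. With the same edit, state how the six 0/1 items in Table 1 form the score (for example a sum, the overall item alone, or the proportion with full marks), because the primary estimate depends on it.

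If the sponsor prefers a test, amend the Study Design statement and pre-specify one primary test at one visit with one model, with all other comparisons labelled exploratory.

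The cost is a few sentences. Enrolment, randomisation and data collection are unchanged. The sponsor gives up either significance claims that Study Design already disclaims or the freedom to choose visit and model afterwards. The documents do not show the study's stage; if outcome data have already been seen, the choice of visit and estimate should be labelled post hoc.
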